# **10. PHARMACOKINETICS**

#### 10.1. Graphical and Tabular Summaries of Pharmacokinetic Profiles

The PK Subset Population will be used when summarizing plasma and lung PK concentrations. Participants enrolled who did not complete dosing will not be included in the PK analysis, but the participant will have concentrations and PK parameters included in listings.

For plasma concentrations, results below the limit of quantification (BQL) collected before the first measurable plasma concentration above the lower limit of quantification (LLOQ) will be treated as zero (0) for plotting, all calculations (including noncompartmental analysis [NCA]) and summary statistics. All other plasma BQL values observed after the first measurable concentration will be treated as missing. Similarly, all BQL lung PK concentrations will be treated as missing. There will be no imputation of missing concentrations. The geometric mean (GM) of concentrations will be treated as missing for sets of data points containing a BQL value.

Collection of plasma or lung samples outside of the protocol defined time window for the timepoint will not result in exclusion of the sample results from NCA. Plasma or lung samples collected out of window will be evaluated on a case-by-case basis. Results from PK samples that were collected substantially outside of the protocol defined time window will be excluded from concentration summary statistics by nominal timepoints and plots of mean concentration by nominal timepoint. Substantially out-of-window samples are defined to be samples that were collected outside twice the size of the protocol required windows and are as follows:  $\pm 10$  min of the nominal timepoint for the 0.5 h, 1, h, and 2 h post-dose samples;  $\pm 20$  min for the 4 h post-dose sample;  $\pm 30$  min for the 8 h and 16 h post-dose samples; and  $\pm 2$  h for the 24 h and 36 post-dose samples on Day 2 and 48 h and 60 h post-dose samples on Day 3.

If the exact time of PK sample collection is not recorded then the collection time will be imputed as the planned time for analysis, as long as it is not known that the sample was collected outside of the protocol defined window. If the exact collection time is not known, but it is known that the sample was collected outside of the protocol defined time window, then the timepoint may be excluded from analysis at the discretion of the PK analyst. Rationale for excluding results from analysis will be described in the CSR. Results from samples with imputed collection times will be indicated in listings of PK sample concentrations.

In the case the bronchoscopy with BAL procedure is delayed, an additional plasma PK sample will be collected within 5 minutes of the last BAL sample. These samples will only be included in the lung PK analysis when calculating the lung PK/plasma PK concentration ratios and PK parameters, and not included in the NCA.

The bioanalytical lab will report concentrations of total and free apramycin in plasma, total apramycin in BAL SUP and BAL AC, and concentrations of urea in plasma in units of  $\mu$ g/mL. All concentrations will be reported in the same units in the CSR. Apramycin concentrations in BAL ELF and BAL AM will be calculated as described in Section 3.3.2. The ratio of free plasma concentration in apramycin to total plasma concentration in apramycin will be calculated to determine the free portion (fu, % unbound) of plasma apramycin. Drug concentrations will be summarized and listed by participant:

- Participant level concentrations of total apramycin and free apramycin in plasma (Listing 35 and Listing 36, respectively).
- Participant level free portion (fu, % unbound) of plasma apramycin (Listing 37).
- Participant level parameters used to derive apramycin concentrations in ELF (see Section 3.3.2.1) and calculated apramycin concentrations in ELF (Listing 39).

- Participant level parameters used to derive apramycin concentrations in AM (see Section 3.3.2.2) and calculated apramycin concentrations in AM (Listing 40).
- Participant level ELF and AM to total apramycin in plasma concentration ratios (Listing 41).
- Participant level BAL cell counts (Listing 42).

Participant level PK parameter concentration listings will include separate columns for concentrations reported by the lab and concentrations used for analysis. The lab reported concentrations may also include codes such as "BQL" and "QNS" (Quantity Not Sufficient), while the analysis concentrations will contain numeric data only, including imputed values, such as 0 for BQL samples collected prior to the first quantifiable sample. Listings will also indicate the nominal time (i.e., the planned sampling timepoint) and the actual post-dose collection time in hours and will note which samples were collected out of window, substantially out of window, or imputed.

PK plasma concentrations of apramycin will be presented in tables and figures by nominal timepoint:

- Individual concentrations in plasma and summary statistics will be presented tabularly for total apramycin in plasma (Table 83) and free apramycin in plasma (Table 84).
- Summary statistics for the free portion of plasma apramycin (fu, % unbound), calculated as the ratio of free to total apramycin concentrations in plasma (Table 85).
- Linear plots of individual participant concentration-time profiles for total apramycin in plasma (Figure 107).
- Semi-log plots of individual participant concentration-time profiles for total apramycin in plasma (Figure 108).
- Linear plots of mean concentration-time profiles for total apramycin in plasma, with error bars representing ± 1 SD (Figure 109).
- Semi-log plots of mean concentration-time profiles for total apramycin in plasma (Figure 110).

Additionally, lung PK (ELF and AM) apramycin concentrations in plasma will be presented in tables and figures by nominal timepoint. ELF and AM concentrations will be calculated as described in Section 3.3.2. For tables and figures of lung PK concentrations that include plasma concentrations, only the plasma samples collected at the same time as the BAL procedure will be used.

- Summary statistics by BAL sampling timepoint for apramycin in ELF concentrations, total apramycin in plasma concentrations, and the concentration ratio of ELF to plasma concentrations will be presented (Table 87).
- Summary statistics by BAL sampling timepoint for apramycin in AM concentrations, total apramycin in plasma concentrations, and the concentration ratio of AM to plasma concentration will be presented (Table 88).
- Plot of individual total apramycin in plasma, ELF, and AM concentrations at each BAL sampling timepoint (Figure 111).
- Linear plots of GM apramycin concentrations by compartment (total apramycin in plasma, apramycin in ELF, and apramycin in AM) at each BAL sampling timepoint (Figure 112).
- Semi-log plots of GM apramycin concentrations by compartment (total apramycin in plasma, apramycin in ELF, and apramycin in AM) at each BAL sampling timepoint (Figure 113).

- Plot of individual ELF and AM to total apramycin in plasma concentration ratios at each BAL sampling timepoint (Figure 114).
- Plot of GM ELF and AM to total apramycin in plasma concentration ratios at each BAL sampling timepoint (Figure 115).

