#### 4.5.2. Pharmacokinetic Variables

A valid liquid chromatography tandem-mass spectrometry (LC-MS/MS) method will be used to determine concentrations of apramycin in plasma and BAL samples as well as urea in plasma and BAL (ELF).

- Blood (Plasma) for apramycin concentrations
  - Blood (plasma) samples for assay of apramycin PK will be collected at the following study days and timepoints: On Day 1 within 30 min before dosing, and 0.5 h (±5 min, immediately at end of infusion), 1 h (±5 min), 2 h (±5 min), 4 h (±10 min), 8 h (±15 min), and 16 h (±15 min) after dosing; on Day 2 at 24 h (±1 h) and 36 h (±1 h) after dosing; and on Day 3 at 48 h (±1 h) and 60 h (±1 h) after dosing.
  - If BAL is delayed, blood (plasma) for apramycin will be collected within the prespecified window of the nominal timepoint and a second sample will be collected within 5 min of the last BAL sample.
- Bronchoscopy with BAL
  - During bronchoscopy with BAL, samples will be obtained at the following timepoints during the study: 0.5 h ± 5 min, 2 h ± 5 min, 4 h ± 10 min, 8 h ±15 min and 24 h ± 1 h after the start of the infusion. Each participant will have a bronchoscopy with BAL at one timepoint only, for a total of 4 samples at each timepoint.
- Urea
  - Urea will be assayed in plasma samples collected at baseline (as part of the total apramycin plasma PK) and at 0.5 h (± 5 min) 2 h (± 5 min), 4 h (± 10 min), 8 h (± 15 min) and 24 h (± 1 h) after the start of the infusion), and in BAL SUP samples corresponding to plasma PK timepoints. If BAL is delayed and a second plasma sample is collected within 5 min of the last BAL sample, plasma urea will be measured only in the second sample.

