#### 14.2 Pharmacokinetics Data

#### Table 83: Total Apramycin Concentrations in Plasma

[Implementation Note: Mark concentrations collected out of window with an asterisk (\*) next to the concentration and include a footnote: "Samples collected out of window are noted by an asterisk (\*)". Mark concentrations collected substantially out of window with two asterisks (\*\*) next to the concentration and include a footnote: "Samples collected substantially out of window are noted by two asterisks (\*\*)". Mark imputed concentration times with three asterisks (\*\*\*) next to the concentration and include a footnote: "Samples collected substantially out of window are noted by two asterisks (\*\*\*)". Mark imputed concentration times with three asterisks (\*\*\*) next to the concentration and include a footnote: "Samples with imputed collection times are noted by three asterisks (\*\*\*)".]

					Ň	lominal Time a (l	n)				
Participant ID	0	0.5	1	2	4	8	16	24	36	48	60
PH2.00123	Х	х	х	х	х	х	х	Х	х	х	Х
PH2.00124	х	х	х	х	х	х	х	Х	х	х	Х
PH2.00125	х	х	х	х	Х	х	Х	Х	х	Х	Х
Statistics	х	х	х	х	Х	х	Х	Х	х	Х	Х
N b	х	х	х	х	Х	х	Х	Х	х	Х	Х
Mean	х	х	х	х	Х	х	Х	Х	х	Х	Х
SD	х	х	х	х	Х	х	Х	Х	х	Х	Х
GM	х	х	х	х	Х	х	Х	Х	х	Х	Х
CV%	х	х	х	х	Х	х	Х	Х	х	Х	Х
Min	Х	Х	Х	X	Х	X	Х	Х	Х	Х	X
Max	Х	X	х	х	х	х	х	х	х	х	Х

Notes: Concentrations are reported in units of  $\mu$ g/ml.

[Out of window footnotes here, if applicable]

a Times are relative to time of dosing.

b Number of data points used to compute the summary statistics. For calculation of summary statistics, BQL values were imputed as 0 if the sample was taken before the first measurable PK sample with a concentration above the LLOQ. BQL values were treated as missing otherwise.

Table with Similar Format:

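### If late plasma samples are below the quantification limit, the arithmetic mean and minimum in SAP Tables 83–84 and the mean in Figures 109–110 describe only the subjects still quantifiable, and read too high

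*SAP*

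**What the plan says.** SAP 10.1 sets plasma BQL results before the first measurable concentration to zero. For later results the rule is: "All other plasma BQL values observed after the first measurable concentration will be treated as missing". It adds: "There will be no imputation of missing concentrations".

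Footnote b of Table 83 (total apramycin in plasma by nominal time) confirms that the rule governs the summary statistics. It defines N as "Number of data points used to compute the summary statistics" and, after describing the zero rule for early samples, says "BQL values were treated as missing otherwise". Table 84 (free apramycin) has the same format.

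One statistic has a safeguard: "The geometric mean (GM) of concentrations will be treated as missing for sets of data points containing a BQL value". Nothing comparable applies to the mean, SD, CV%, minimum or maximum in the same table, or to the mean profiles in Figures 109 and 110. No minimum share of quantifiable values is required before a mean is shown. The last plasma samples are drawn "on Day 3 at 48 h (±1 h) and 60 h (±1 h) after dosing".

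**The concern.** Treating late BQL values as missing is a usual choice for individual noncompartmental analysis. A summary across subjects is different, because the values removed are exactly the lowest ones. Every dropped value lies below every retained one, so the mean of the remainder can only be too high and the printed minimum can never fall below the LLOQ. SD and CV% likewise describe only the quantifiable subset.

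The SAP recognises this for the geometric mean but not for its neighbours. At a late timepoint Table 83 could therefore show an arithmetic mean of a few remaining subjects beside a blank geometric mean. Figures 109–110 would plot that mean with no count beside it, which flattens the tail of the average curve. Plasma concentration is named among the primary endpoints (SAP 3.2), and the mean profile is one of its main displays.

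**Working it through.** **Inputs from the documents.** Up to 20 subjects, in 5 cohorts of 4 (SAP 5), are pooled across cohorts (SAP 6.1). Total plasma apramycin is sampled to 60 h; free apramycin is measured only at 0.5 and 36 h. The only variability figure is an AUC CV below 20% in the first-in-human study (Protocol 2.4.1).

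**Not in the documents.** LLOQ, human half-life, the expected share of BQL values, and the spread of concentrations at late times. There is no planned figure to reproduce, so what follows is a range under stated assumptions.

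**Formula.** Let concentrations at a timepoint be lognormal with s² = ln(1 + CV²), let f be the fraction BQL, and let z(f) be the standard normal quantile. The mean after dropping BQL values, divided by the true mean, is

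R = Φ(s − z(f)) / (1 − f).

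**CV 20%:** s = √ln(1.04) = 0.198.
- f = 25%: z = −0.674, Φ(0.873) = 0.809, R = 0.809/0.75 = 1.08.
- f = 50%: z = 0, Φ(0.198) = 0.578, R = 0.578/0.50 = 1.16.

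**CV 40%:** s = √ln(1.16) = 0.385.
- f = 25%: Φ(1.060) = 0.855, R = 0.855/0.75 = 1.14.
- f = 50%: Φ(0.385) = 0.650, R = 0.650/0.50 = 1.30.

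| CV (assumed) | 10% BQL | 25% BQL | 50% BQL |
|---|---|---|---|
| 20% | 1.03 | 1.08 | 1.16 |
| 40% | 1.06 | 1.14 | 1.30 |
| 60% | 1.07 | 1.19 | 1.42 |
| 100% | 1.09 | 1.25 | 1.60 |

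With f = 0 the ratio is 1.

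**How often the two statistics part company.** With 20 subjects and a 10% chance of BQL each, the probability of at least one BQL value is 1 − 0.9²⁰ = 0.88. The geometric mean would then usually be blank while the arithmetic mean is printed.

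**Which times are affected.** In a mono-exponential simulation (assumed starting concentration 100 µg/mL, log-SD 0.2 on both starting concentration and half-life, LLOQ 0.1 µg/mL), the answer depends on half-life:
- Half-life 4 h: 28% BQL at 36 h (ratio 1.34) and 81% at 48 h (ratio 3.6).
- Half-life 8 h: no material bias through 48 h; at 60 h, 7% BQL and ratio 1.07.

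**Figures.** The implementation notes for Figures 109–110 ask for different symbols and line types by cohort, although SAP 6.1 says no analyses are done by cohort. If the means are drawn by cohort, each rests on at most 4 subjects and one BQL value removes 25% of the data.

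**LLOQ/2 as an alternative.** At CV 40% it gives 0.95 of the true mean with 25% BQL and 0.88 with 50%, closer than dropping. At CV 20% it gives 0.92 and 0.82, against 1.08 and 1.16 for dropping, so it is no better there. It replaces an upward bias with a downward one.

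**The case against.** The strongest reply is that little depends on these means. Cmax, AUC, Ke and half-life come from each subject's own profile (SAP 10.2). The lung/plasma exposure ratios use geometric means at the BAL timepoints, nominally no later than 24 h (SAP 10.2.1). No hypothesis is tested. All of that stands. A reader might infer from a flattened mean curve that the reported half-life or primary exposure parameters are biased; the documents do not support that, because none of those quantities uses the arithmetic mean.

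A second reply is that the loss is visible. Table 83 prints individual values and N and footnotes the rule. Listing 35 shows the laboratory result beside the analysis value, and Figures 107–108 show individual profiles. This stands for the tables. It does not help Figures 109–110, whose specifications mention neither N nor a BQL count.

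A third reply is that BQL values may not occur. A reader might infer that the means at 36, 48 and 60 h will be inflated. The documents do not establish this. Scheduling the free-apramycin assay at 36 h (Protocol 8.5.2) suggests that quantifiable levels are expected then.

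A reader might also quote far larger factors. A geometric mean at half the LLOQ with CV 50% (s = 0.472) gives a ratio of about 2.2. But ln 2/0.472 = 1.47 leaves only 7.1% of values above the LLOQ. About 93% of subjects would be BQL, and 20 × 0.071 ≈ 1.4 would remain. That is not a fair headline.

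**Conclusion.** The point holds as a conditional one about descriptive reporting. If any late plasma sample is BQL, the direction of the distortion is certain: the arithmetic mean and minimum are too high. The size for the mean is about 8% at 25% BQL and 16% at 50% BQL for CV 20%, and 14% and 30% for CV 40%. It is zero if every sample through 60 h is quantifiable.

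These figures assume lognormal concentrations. The lower CV borrows the first-in-human upper limit for AUC, and late concentrations may vary more than AUC. That 48–60 h are the exposed times for total apramycin is an assumption; for free apramycin the only late time is 36 h. The matter is minor, but it is avoidable and always errs in one direction.

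**What to change.** Keep the missing rule for noncompartmental analysis. For Tables 83–84:

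- Add a row with the number BQL at each timepoint.
- Add the median with BQL values ranked lowest, printed as BQL if it falls there. SAP 6.1 already lists the median for continuous data; the Table 83 shell omits it.
- Print the minimum as BQL when any value is BQL.
- Do not print the arithmetic mean and SD when more than half the values are BQL. When fewer are, flag them as based on quantifiable values only. Say which rule CV% follows.

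Apply the same withholding and flagging rule to Figures 109–110. Imputing LLOQ/2 is optional and only as a sensitivity summary, since it has its own downward bias and departs from the SAP's rule against imputation.

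The cost is a few extra table rows, revised footnotes, and some late mean points not shown. NCA and the listings' analysis values do not change. SAP 15 allows an addendum before final data lock.

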### **10.2.** Noncompartmental Analysis

PK parameters for plasma and lung PK data will be estimated through NCA using version 8.2 or higher of Phoenix WinNonlin®. Actual post-dose times will be used for the estimation of plasma PK parameters, and nominal time will be used for the estimation lung (ELF and AM) PK parameters. In the case of unknown sample collection times, the imputed time will be included in NCA. Any outliers identified in the PK analysis will be discussed in the analysis report. Outliers will not be excluded from the PK analysis.

Individual plasma PK parameter estimates for total apramycin will be listed (Listing 38). Plasma PK parameters will be summarized in Table 86 for total apramycin. Summary statistics will include mean, SD, min, max, GM, and coefficient of variation as a percent (CV%).

The CV% will be calculated using the method for log-normally distributed data:

$$CV\% = \sqrt{\exp(s^2) - 1} \times 100\%$$

Where  $s^2$  is the variance of the natural log-transformed data.

Phoenix WinNonlin NCA will use the following settings to compute parameters from plasma and lung PK data:

- Linear Up Log Down calculation method
- Uniform weighting
- IV infusion
- Lambda Z Acceptance Criteria
  - $\circ$  Rsq\_adjusted  $\geq 0.90$
  - $\circ$  Span  $\geq$  3 half-lives
  - $\circ$  Includes at least 3 timepoint after Tmax

If an insufficient number of participants meet the Lambda Z Acceptance Criteria for computing PK parameters, then relaxed Lambda Z Acceptance Criteria may be used and will be described in the CSR.

#### Cmax

 $C_{max}$  is defined as the maximum drug or concentration observed over all PK sample concentrations. It will be obtained from the **Cmax** parameter calculated by WinNonlin. If there is no measurable concentration in the participant's PK profile, then  $C_{max}$  will be missing for that participant.  $C_{max}$  will be reported in units of  $\mu g/mL$ .

#### Tmax

Time of maximum concentration  $(T_{max})$  is defined as the time at which the  $C_{max}$  occurs. It will be obtained from the **Tmax** parameter calculated by WinNonlin. If there is no measurable  $C_{max}$  in the participant's PK profile, then  $T_{max}$  will be missing for that participant.  $T_{max}$  will be reported in units of h.

#### Ke

The terminal phase elimination rate constant (Ke) is defined as the first-order rate constant describing the rate of decrease of drug or metabolite concentration in the terminal phase (defined as the terminal region of the PK curve where drug or metabolite concentration follows first-order elimination kinetics). Ke will be computed as the slope of a terminal region consisting of  $\geq$  3 successive points in the plot of log-transformed concentration data versus time. Ke will be estimated using uniform weighting.

Timepoints used in the estimation of  $K_e$  will be initially selected using the WinNonlin automatic algorithm. Manually chosen timepoints may be used at the discretion of the PK analyst after examination of the automatically chosen points in the context of the semi-log profile to improve estimation of  $K_e$  on a case-by-case basis. The set of points chosen must satisfy the Lambda Z Acceptance Criteria described above. Otherwise, the elimination rate constant and all derived parameters (apparent terminal elimination half-life  $[t_{1/2}]$ , AUC Extrapolated to Infinity  $[AUC_{(0-\infty)}]$ , clearance [CL], and volume of distribution  $[V_d]$ ) will be treated as missing.

Drug concentration used to calculate  $K_e$  will be indicated in Listing 35. This parameter will be obtained from the Lambda\_z parameter calculated by WinNonlin. Ke will be reported in units of 1/h.

**t**½

The  $t_{1/2}$  is defined as the time required for the drug or metabolite concentration to decrease by a factor of onehalf in the terminal phase. The  $t_{1/2}$  can be estimated as  $\ln(2)/K_e$ . It will be obtained from the **HL\_Lambda\_z** parameter calculated by WinNonlin. Half-life will be reported in units of h. If the Lambda Z Acceptance Criteria is not met,  $t_{1/2}$  will be treated as missing.

#### AUC

 $AUC_{(0-8)}$  and  $AUC_{(0-24)}$  are defined as the areas under the concentration-time curve from dosing (time 0) to 8 h and 24 h post infusion start, respectively.  $AUC_{(0-last)}$  is defined as the area under the concentration-time curve from dosing (time 0) to the time of the last measured concentration.  $AUC_{(0-8)}$ ,  $AUC_{(0-24)}$ , and  $AUC_{(0-last)}$  will be estimated using the Linear Up Log Down calculation method and obtained from the **AUClast** parameter calculated by WinNonlin (for  $AUC_{(0-8)}$  and  $AUC_{(0-24)}$ , data will be subset to only include results collected up to and including the 8 h and 24 h post-dose timepoint, respectively, and a separate NCA will be run).

 $AUC_{(0-\infty)}$  is defined as the total area under the concentration-time curve from dosing (time 0) taken to the limit as the end time becomes arbitrarily large.  $AUC_{(0-\infty)}$  can be calculated by adding  $AUC_{(0-last)}$  to an extrapolated value equal to the last measured concentration greater than the LLOQ divided by Ke:

$$AUC_{(0-\infty)} = AUC_{(0-last)} + \frac{C_{last}}{K_e}$$

Where  $C_{last}$  is the last measured concentration  $\geq$  LLOQ. AUC(0-∞) will be obtained from the AUCINF\_obs parameter calculated by WinNonlin®. If the Lambda Z Acceptance Criteria are not met, AUC(0-∞) will be treated as missing.

 $%AUC_{ex}$  is defined as percentage of  $AUC_{(0-\infty)}$  obtained by extrapolation from time of the last measured concentration to infinity.  $%AUC_{ex}$  can be calculated by dividing AUC from time of the last measured concentration to infinity by  $AUC_{(0-\infty)}$ :

$$\% AUC_{ex} = \frac{AUC_{(0-\infty)} - AUC_{(0-last)}}{AUC_{(0-\infty)}},$$

- 43 -**Restricted**  If %AUCex is >20% or the Lambda Z Acceptance Criteria is not met, the estimated AUC(0- $\infty$ ) will be excluded from statistical summaries of PK parameter estimates and downstream calculations. %AUCex will be obtained from the **AUC\_%Extrap\_obs** parameter calculated by WinNonlin.

All AUCs will be reported in units of  $\mu g^{*}h/mL$ .

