# 4 STUDY DESIGN

This is a Phase 1, single center, open-label, study to evaluate the plasma and lung pharmacokinetics (PK), safety and tolerability of a single intravenous (IV) dose of apramycin in twenty healthy male and female subjects 18 to 45 years of age (inclusive).

Each subject will be enrolled to one of five cohorts (T1-T5) before dosing on Day 1. Four subjects will be allocated to each cohort. Each cohort corresponds to the timepoint after dosing when a single bronchoscopy with bronchoalveolar lavage (BAL) will be performed: 0.5 h (± 5 min) (Cohort T1), 2 h (± 5 min) (Cohort T2), 4 h (± 10 min) (Cohort T3), 8 h (± 15 min) (Cohort T4), and 24 h ( $\pm$  1 h) (Cohort T5). The timing of bronchoscopy and BAL in cohort T5 is nominal. The final timepoint will be determined after analysis of apramycin concentrations in BAL. If apramycin is detectable in BAL collected from cohorts T1-T4, then T5 will be enrolled. If it is not detectable, then cohort T5 will not be enrolled. Blood will be collected at several timepoints to 60 hours after dosing (see collection schedule in Section 8.5.1) and will include samples that will coincide with BAL collections. The concentration and PK exposure parameters  $(C_{\text{max}} \text{ and } AUC_{(0-t)})$  of total apramycin in epithelial lining fluid (ELF) and alveolar macrophages (AM), collected through BAL, and in plasma collected at the scheduled timepoints to 8 h after dosing, will be evaluated from the first four cohorts, T1-T4, to determine if apramycin penetrates into the lung tissues and dosing of the T5 cohort is warranted. If cohort T5 is dosed, the final concentration and PK analysis of apramycin in BAL samples and plasma will include data from all T1-T5 cohorts.

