Subjects will participate in the study for approximately 58 days, including a 28-day screening period, consisting of an out-patient period of 26 days (Day -28 to Day -3) with 1 to 2 site visits and 2 inpatient days, Day -2 and Day -1, to confirm eligibility, enroll and complete baseline assessments; a 3-day in-patient treatment period, with treatment administered on Day 1, bronchoscopy with BAL done within 24 h after dosing, and in-patient follow up completed on Days 2 and 3; and a 27-day out-patient follow-up period with site visits on Day 14 ( $\pm$  3 days) and Day 30 ( $\pm$  4 days), the last follow up visit. It is anticipated that the duration of the study will be about 6 months to enroll Cohorts T1-T4 and 10 months to complete Cohort T5, if enrolled, following an interim data analysis to review lung PK data.

Enrollment will be rolling and will be coordinated with the bronchoscopy service. Tentative reservations will be made and confirmed once subject eligibility is determined. Enrollment and treatment of subjects will be staggered and no more than two subjects will be dosed on a single day not less than 2 hours apart. Additional subjects may also be admitted to the Clinical Trial Unit (CTU) before dosing and may serve as back-up study subjects. A subject assigned to one of the T1 to T4 cohorts may be reassigned to another cohort depending on the availability of a bronchoscopy time slot. (See Section 5.3.1)
DMID Protocol 20-0012	Version 5.0
Apramycin	10 July 2023

Apramycin will be reconstituted in sterile normal saline and a 30 mg/kg dose will be administered as a single IV infusion in a forearm vein over 30 min ( $\pm$  5 min) using a syringe or infusion pump. (See Section 6.2 for DP preparation and administration).

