# 6.6. Interim Analyses and Data Monitoring

An interim analysis of PK data is planned to follow the completion of Cohort T4 (see Section 6.2). Concentration-time data will be presented tabularly and graphically for participants in the PK Analysis Population for both plasma and BAL (ELF and AM) apramycin concentrations. Non-compartmental analysis (NCA) PK parameters will be summarized for the plasma and BAL PK data. Tables and figures for analyses described in Section 10 will be used for the interim analysis. An SMC meeting to review cumulative safety data is planned after Cohort T4. Safety data, including TEAEs, SAEs, clinical laboratory results (CHEM, HEM, COAG, and UA), VS, ECGs, and audiology testing results will be presented. The SMC may also review safety data during an *ad hoc* meeting if a halting rule (see Protocol v3.0 Section 9.5) is met.

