#### 10.2.1. Ratio of Lung PK to Plasma PK

Only plasma samples collected at the same time as the BAL procedure will be used in the calculations of the Lung PK to Plasma PK ratios. The GM concentrations of apramycin in ELF, AM, and plasma from the BAL sampling timepoints will be used to estimate the population average  $C_{max}$ ,  $AUC_{(0-\infty)}$ ,  $AUC_{(0-24)}$ , and  $AUC_{(0-last)}$ .  $AUC_{(0-\infty)}$ ,  $AUC_{(0-24)}$ , and  $AUC_{(0-last)}$  will be estimated using the Linear Up Log Down calculation method. Since the calculated concentrations used at each timepoint will be based on measurements from multiple participants, nominal timepoints will be used when estimating these parameters.

The population estimates of AUC(0-24), AUC(0-t), AUC(0- $\infty$ ), Cmax, Tmax, and t1/2 for apramycin in ELF and AM will be presented in Table 89. The population estimates of Cmax, AUC(0- $\infty$ ), AUC(0-24), and AUC(0-last) in plasma, ELF, and AM, as well as the ratios of ELF-to-plasma and AM-to-plasma exposure parameters will be presented in Table 90 for total apramycin.

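### With no 24-h geometric mean, the SAP rule prints a shorter area as AUC(0-24), and the lung/plasma AUC ratio has no stated common end time

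*SAP*

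**What the plan says.** SAP 10.2 (AUC) defines AUC(0-8) and AUC(0-24) as areas to 8 h and 24 h after infusion start. It obtains both from AUClast in separate runs on truncated data: "data will be subset to only include results collected up to and including the 8 h and 24 h post-dose timepoint". The same section ends AUC(0-last) at the last measured concentration.

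SAP 10.2.1 builds the population AUCs and the lung/plasma ratios from one profile per matrix: "The GM concentrations of apramycin in ELF, AM, and plasma from the BAL sampling timepoints will be used to estimate the population average". It uses nominal times and only plasma samples paired with the lavage (BAL). SAP 10.1 adds: "The geometric mean (GM) of concentrations will be treated as missing for sets of data points containing a BQL value".

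The 24-h point belongs to T5 alone. Protocol section 4 leaves its time open: "The final timepoint will be determined after analysis of apramycin concentrations in BAL". The same section says "bronchoscopy with BAL done within 24 h after dosing", so apart from the ±1 h window the time can only move earlier. At the T1-T4 interim, SAP 6.6 says "Tables and figures for analyses described in Section 10 will be used for the interim analysis". For that stage Protocol section 4 names only Cmax and AUC(0-t), with concentrations "in plasma collected at the scheduled timepoints to 8 h after dosing, will be evaluated from the first four cohorts, T1-T4".

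Tables 89 and 90 have rows for AUC(0-24), AUC(0-last) and AUC(0-∞). Neither has a row for AUC(0-8), although SAP 10.2 defines it.

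**The concern.** The lung/plasma AUC(0-24) ratio is a primary outcome measure. Its definition fixes the end time at 24 h, but its computation does not. SAP 10.2 says when AUC(0-∞) is to be treated as missing. It gives no such rule for AUC(0-24), and SAP 10.2.1 does not say what to do when one matrix lacks a 24-h geometric mean.

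Two errors are then possible:

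- **Wrong label.** Lung and plasma both stop at the same earlier time, and the result is printed as AUC(0-24).
- **Mismatched ratio.** One matrix runs to 24 h and the other stops at 8 h.

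At stake is whether a figure headed AUC(0-24) can be compared with other 24-h exposures or carried into later work on the drug.

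**Working it through.** The plan states no AUC, half-life or quantification limit, so there is no figure to reproduce.

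**Step 1: no assumptions needed.** The area is a sum of trapezoids over the available times among 0.5, 2, 4, 8 and 24 h, starting from zero at time 0. If the last geometric mean is at 8 h, the value printed as AUC(0-24) is A(0-8), which is also AUC(0-last). The missing part is A(8-24) = (C8 − C24) × 16 / ln(C8/C24).

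**Step 2: inputs for size.**

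- From the SAP: linear-up/log-down rule, IV infusion, nominal times.
- From the protocol: 0.5 h infusion.
- Assumed: one-compartment plasma, half-life h = 2, 2.5 or 3 h, k = ln2/h; lung following dL/dt = q(P − L), q = ln2/(lung half-life), with lung half-life 0.25, 0.5 or 1 h, and 3 h as a sensitivity case. The lung scale cancels in every percentage.

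**Step 3: plasma at h = 3 h, with C0.5 = 100.** k = 0.2310; C8 = 100 × 2^(−7.5/3) = 17.68; C24 = 100 × 2^(−23.5/3) = 0.44.

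- A(0-0.5) = 0.5 × 100/2 = 25.0
- A(0.5-8) = (100 − 17.68)/0.2310 = 356.3
- A(8-24) = (17.68 − 0.44)/0.2310 = 74.6

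So A(0-8) = 381.3 and A(0-24) = 455.9. The shortfall is 74.6/455.9 = 16.4%.

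**Step 4: lung at lung half-life 1 h, same plasma.** L(t) = S(t) − S(t − 0.5), where S(t) = 1 − e^(−qt) − [q/(q − k)](e^(−kt) − e^(−qt)) for t > 0 and S = 0 otherwise. On the same scale, L at 0.5, 2, 4, 8 and 24 h is 15.8, 58.6, 55.0, 25.8 and 0.66. The segments are 3.9, 55.8, 113.5, 154.2 and 109.5.

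- A(0-8) = 327.4; A(0-24) = 437.0
- Ratio over 0-24 h: 437.0/455.9 = 0.958
- Ratio over 0-8 h: 327.4/381.3 = 0.859, which is 10.4% lower

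**Step 5: all cases, relative to the matched 0-24 h value.**

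| Plasma half-life | Plasma area to 8 h | Lung area to 8 h (lung 0.25-1 h) | Ratio, both to 8 h (lung 0.25-1 h) | Ratio, both to 8 h (lung 3 h) | Lung 0-24 h over plasma 0-8 h |
|---|---|---|---|---|---|
| 2 h | −6.8% | −8.4% to −13.6% | −1.7% to −7.3% | −30% | +7.3% |
| 2.5 h | −11.6% | −13.6% to −19.6% | −2.3% to −9.1% | −32% | +13.1% |
| 3 h | −16.4% | −18.7% to −25.1% | −2.8% to −10.4% | −33% | +19.6% |

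The last column is A(0-24)/A(0-8) for plasma alone, for example 455.9/381.3 = 1.196, so it does not depend on the lung model.

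**Step 6: T5 moved earlier.** With lung half-life 0.25-1 h, the ratio is 0.4-3.5% low if T5 is at 12 h and 0.1-1.1% low at 16 h. With lung half-life 3 h, the same formulas give about 12-14% and 4-5%.

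**Step 7: what the mismatch needs.** The plasma quantification limit must lie between the 24-h and 8-h levels. As a share of the 0.5-h level, that is 0.03% to 7% at a plasma half-life of 2 h, and 0.4% to 18% at 3 h.

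**The case against.** The best defence is that the plan closes most routes to harm.

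- **Common grid.** All three matrices use the same nominal lavage times. With five geometric means in each, every area ends at 24 h. This stands; the gap is only the missing rule for a lost point.
- **Lavage values below quantification.** A reader might infer that one such value at 24 h leaves lung at 0-8 h over plasma at 0-24 h. The documents do not support this. SAP 6.3.2.1 requires quantifiable lavage values, and SAP Table 11 carries that exclusion through to the PK subset. The participant leaves with the paired plasma. Only a strained use of the case-by-case clause in SAP 6.3.2.3 would reopen it.
- **T5 not enrolled.** A reader might expect mislabelled final tables here too. Protocol section 4 skips T5 only when drug is undetectable in lavage: "If it is not detectable, then cohort T5 will not be enrolled". There is then no lung AUC to mislabel.
- **Visibility.** A reader might think that the tables would hide a lost 24-h set. They would not. Table 90 prints N by matrix (20 − 4 = 16 for plasma beside 20 for lung), and Tables 87-88 show the 24-h columns side by side. The reader would still have to work out the end time.
- **When evaluable.** Protocol 11.4.4.3 computes ratios only when evaluable, so an analyst could leave the interim row blank. But no criterion is given for AUC(0-24), and AUClast still returns a number.
- **Late plasma values.** Plasma is sampled to 60 h and free drug is measured at 36 h, so an unquantifiable 24-h plasma value is evidently not expected. This stands and makes the mismatched ratio unlikely.

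**Conclusion.** The point holds as a conditional one and should be fixed. As written, the rule prints a shorter area as AUC(0-24) whenever the 24-h geometric mean is absent. That occurs at the T1-T4 interim if the rows are filled as SAP 6.6 directs, and at the final analysis if T5 is moved earlier. In both cases lung and plasma cover the same interval, so the fault is the label. It does not touch the T5 decision, which rests on detectability.

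The mislabelling follows from the text alone; its size does not. Under the assumed plasma half-lives of 2-3 h, the interim ratio falls 2-10% short of the 0-24 h ratio for lung half-lives of 0.25-1 h, and 30-33% short at 3 h. The mismatched case, lung to 24 h over plasma to 8 h, would overstate the ratio by 7-20%, but it needs an unlikely pattern of unquantifiable values. The AUC(0-last) ratio has the same gap, since each matrix may end at its own last value.

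**What to change.** 1. In SAP 10.2 and 10.2.1, report AUC(0-24) and its ratio only when a 24-h geometric mean exists in both matrices. Otherwise report it as not estimable.
2. Compute each lung/plasma AUC ratio, including AUC(0-last), over one common interval ending at the last lavage time with a geometric mean in both matrices. Print that end time with the ratio.
3. Add the already-defined AUC(0-8) as a row in Tables 89 and 90, and use it at the T1-T4 interim.
4. Note in SAP 6.3.2.3 that the case-by-case clause does not override the requirement for quantifiable lavage values in SAP 6.3.2.1.

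The cost is SAP wording and one added row in each of the two tables; no sampling or participants are added. The downside is that AUC(0-24), a primary measure, may have to be reported as not estimable.
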